2.1.1 Phase I run in

Both drugs are FDA approved for other disease indications, with safety and tolerability well described at the approved doses. Therefore the limited phase I portion of this study aims to

assess the safety and tolerability of this drug combination at their established doses. There will be no dose escalation cohorts within this phase I run in group.

The first six patients will constitute the phase I portion of this study. These initial 6 patients may come from either cohort and will be assessed for dose limiting toxicities (DLTs, defined in Section 2.1.1.1) after completion of cycle #1. After these first 6 patients initiate cycle #1, enrollment to the study will be temporarily halted, and a formal DLT evaluation of all 6 patients will be conducted.

If ≤ 2 of these six patients experience DLTs after completion of cycle #1, then the study will proceed to the phase II portion, using MK-3475 200mg IV Q21 days and Vorinostat 400mg PO 5 out of 7 days (x 3 weeks) of each 21 day cycle.

If > 2 of these first 6 patients experience a DLT upon completion of cycle #1, the study will proceed to the phase II portion using MK-3475 IV 200mg Q28 days Vorinostat 300mg daily 5 out of 7 days (x 4 weeks) of each 28 day cycle.

Only upon completion of the DLT evaluation for these first 6 patients and the determination of appropriate Phase II dose, will enrollment reopen for the phase II expansion.

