2.1.1.1 Definition of Dose-Limiting Toxicities

All toxicities will be graded using National Cancer Institute (NCI) CTCAE Version 4.0 (see Appendix).

The occurrence of any of the following toxicities during Cycle 1 will be considered a DLT, if judged by the Investigator to be possibly, probably or definitely related to study drug administration:

- 1. Grade 4 non-hematologic toxicity (not laboratory)
- 2. Grade 3 non-hematologic toxicity (not laboratory) lasting >3 days despite optimal supportive care.
- 3. Any Grade 3 or Grade 4 non-hematologic laboratory value if:
 - Medical intervention is required to treat the patient, or
 - The abnormality leads to hospitalization
- 4. Grade 3 or Grade 4 febrile neutropenia:
 - Grade 3 is defined as ANC <1000/mm3 with a single temperature of >38.3 degrees C (101 degrees F) or a sustained temperature of ≥38 degrees C (100.4 degrees F) for more than one hour
 - Grade 4 is defined as ANC <1000/mm3 with a single temperature of
- >38.3 degrees C (101 degrees F) or a sustained temperature of \ge 38 degrees C (100.4

degrees F) for more than one hour, with life-threatening consequences and urgent intervention indicated.

5. Prolonged delay (>2 weeks) in initiating cycle 2 due to treatment-related toxicity

- 6. Hematologic toxicity requiring dose modifications as outlined in Section 5.1.2.4
 - 7. Grade 5 toxicity.

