5.6 Rescue Medications & Supportive Care

5.6.1 Supportive Care Guidelines Specific for MK-3475

Subjects should receive appropriate supportive care measures as deemed necessary by the treating investigator including but not limited to the items outlined below:

• Anti-infectives: Subjects with a documented infectious complication should receive oral or IV antibiotics or other anti-infective agents as considered appropriate by the treating investigator for a given infectious condition, according to standard institutional practice.

- Immune-related adverse events: Please see Section 5.6.1.1 below and the separate Pembrolizumab ECI guidance document regarding diagnosis and management of adverse experiences of a potential immunologic etiology.
- Management of Infusion Reactions: Acute infusion reactions (which can include cytokine release syndrome, angioedema, or anaphylaxis) are different from allergic/hypersensitive reactions, although some of the manifestations are common to both AEs. Signs and symptoms usually develop during or shortly after drug infusion and generally resolve completely within 24 hours of completion of infusion. Signs/symptoms may include: Allergic reaction/hypersensitivity (including drug fever); Arthralgia (joint pain); Bronchospasm; Cough; Dizziness; Dyspnea (shortness of breath); Fatigue (asthenia, lethargy, malaise); Headache; Hypertension; Hypotension; Myalgia (muscle pain); Nausea; Pruritis/itching; Rash/desquamation; Rigors/chills; Sweating (diaphoresis); Tachycardia; Tumor pain (onset or exacerbation of tumor pain due to treatment); Urticaria (hives, welts, wheals); Vomiting.

Table 5 below shows treatment guidelines for subjects who experience an infusion reaction associated with administration of MK-3475.

NCI CTCAE Grade	Treatment	Premedication at subsequent dosing
Grade 1 Mild reaction; infusion interruption not indicated; intervention not indicated	Increase monitoring of vital signs as medically indicated until the subject is deemed medically stable in the opinion of the investigator.	None

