Grade 2 Requires infusion interruption but responds promptly to symptomatic treatment (e.g., antihistamines, NSAIDS, narcotics, IV fluids); prophylactic medications indicated for < =24 hrs	Stop Infusion and monitor symptoms. Additional appropriate medical therapy may include but is not limited to: IV fluids Antihistamines NSAIDS Acetaminophen Narcotics Increase monitoring of vital signs as medically indicated until the subject is deemed medically stable in the opinion of the investigator. If symptoms resolve within one hour of stopping drug infusion, the infusion may be restarted at 50% of the original infusion rate (e.g. from 100 mL/hr to 50 mL/hr). Otherwise dosing will be held until symptoms resolve and the subject should be premedicated for the next scheduled dose. Subjects who develop Grade 2 toxicity despite adequate premedication should be permanently discontinued from	Subject may be premedicated 1.5h (± 30 minutes) prior to infusion of MK-3475 with: Diphenhydramine 50 mg po (or equivalent dose of antihistamine). Acetaminophen 500-1000 mg po (or equivalent dose of antipyretic).

Table 5 Infusion Reaction Treatment Guidelines

NCI CTCAE Grade	Treatment	Premedication at subsequent dosing
	further trial treatment administration.	
Grades 3 or 4		
Grade 3:	Stop Infusion.	
Prolonged (i.e., not rapidly	Additional appropriate medical therapy may	No subsequent dosing
responsive to symptomatic	include but is not limited to:	
medication and/or brief	IV fluids	
interruption of infusion);	Antihistamines	
recurrence of symptoms following	NSAIDS	
initial improvement;	Acetaminophen	
hospitalization indicated for other	Narcotics	
clinical sequelae (e.g., renal	Oxygen	
impairment, pulmonary infiltrates)	Pressors	
	Corticosteroids	
Grade 4:	Epinephrine	
Life-threatening; pressor or		
ventilatory support indicated	Increase monitoring of vital signs as	
	medically indicated until the subject is	
	deemed medically stable in the opinion of	
	the investigator.	
	Hospitalization may be indicated.	
	Subject is permanently discontinued	
	from further trial treatment	
A	administration.	
	t should be available in the room and a physicia	in readily available during the
period of drug administration.	r to the Common Terminalogy Criteria for Ad-	α
-	r to the Common Terminology Criteria for Adv	erse Evenis v4.0 (CICAE) at
http://ctep.cancer.gov		

5.6.1.1 Supportive Care Guidelines for Events of Clinical Interest and Immune-related Adverse Events (irAEs)

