5.9 Subject Replacement Strategy

Replacement of Patients in DLT Period

Patients who received <90% of the MK-3475 infusion in Cycle 1 (e.g., because the infusion had to be discontinued due to an infusion reaction) and did not experience a DLT will not be taken into account in the assessment of the overall DLT rate for the phase I run in cohort and need to be replaced.

If a patient experiences a DLT in Cycle 1, study therapy may be discontinued following discussion and agreement between the Sponsor and Investigator. An alternative consideration may be dose modifications of Vorinostat and MK-3475 as described in Section 5.2.1.2 with continued therapy.

Specific procedures to be performed during the trial, as well as their prescribed times and associated visit windows, are outlined in the Trial Flow Chart - Section 6.0. Details of each procedure are provided in Section 7.0 - Trial Procedures.

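### The run-in decision can leave out a treatment-ending grade 3 infusion reaction that stops the Cycle 1 infusion before 90% and resolves within 3 days, unless DLT criterion 5 is read to cover a cycle 2 never started

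*Combined protocol and SAP*

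**What the plan says.** **The gate.** Section 2.1.1 assesses six patients for DLTs. "If ≤ 2 of these six patients experience DLTs after completion of cycle #1", phase II uses the starting regimen. "If > 2 of these first 6 patients experience a DLT upon completion of cycle #1", it uses the fallback regimen.

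**The DLT list (Section 2.1.1.1).** Three criteria could apply to a related infusion reaction that is not fatal:
- criterion 1: "Grade 4 non-hematologic toxicity (not laboratory");
- criterion 2: "Grade 3 non-hematologic toxicity (not laboratory) lasting >3 days despite optimal supportive care";
- criterion 5: "Prolonged delay (>2 weeks) in initiating cycle 2 due to treatment-related toxicity".

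**Infusion reactions (Section 5.6.1 and Table 5).** The text says that signs and symptoms "generally resolve completely within 24 hours of completion of infusion". For grade 3 or 4, Table 5 stops the infusion and permanently discontinues trial treatment; its entry on premedication at later doses reads "No subsequent dosing". Section 5.2.1.2 does not allow either drug to be continued alone.

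**Replacement (Section 5.9).** The rule applies to patients who received under 90% of the Cycle 1 infusion. Its example is an infusion cut short: "because the infusion had to be discontinued due to an infusion reaction) and did not experience a DLT will not be taken into account". Such patients do not enter the DLT rate and are replaced. The example is not limited by the grade of the reaction or by whether further dosing is allowed.

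**The concern.** Each of these rules is reasonable alone. Read together, they let one kind of toxicity fall out of the run-in decision. The protocol regards a grade 3 infusion reaction as severe enough to end treatment with both drugs. If it is brief and cut the infusion short, however, it may count neither as a DLT nor in the denominator, and another patient takes the place.

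The result fits poorly with criterion 5. A related toxicity that delays cycle 2 by more than two weeks counts towards the fallback, while one that rules cycle 2 out altogether may not. Safety and tolerability is the primary objective (Section 3.1), and the six-patient rule is the only formal gate between the two regimens. Because the exclusion is caused by the study drug, it is informative. The run-in DLT rate would describe patients selected partly for having tolerated the first infusion.

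**Working it through.** The documents give no operating characteristics for the run-in, so there is no figure of theirs to reproduce. The check has three steps.

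**1. Which patients fall through**

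| Related infusion reaction in Cycle 1 | DLT? | Replaced under 5.9? |
|---|---|---|
| Grade 4 | Yes, criterion 1 | No |
| Grade 3, lasting more than 3 days | Yes, criterion 2 | No |
| Grade 3, 3 days or less, 90% or more infused | Not by criteria 1 or 2; criterion 5 unclear | No, stays in the denominator |
| Grade 3, 3 days or less, under 90% infused | Not by criteria 1 or 2; criterion 5 unclear | Yes, if criterion 5 is not met |

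Only the last row is lost from both numerator and denominator.

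**2. Whether the loss can change the decision**

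Suppose the first six patients include two DLTs and one patient from the last row.
- Counted: 2 + 1 = 3 of 6, which exceeds 2, so the fallback regimen follows.
- Replaced: 2 DLTs plus whatever the replacement shows. The starting regimen is kept with probability 1 − p, where p is the chance of a DLT in the replacement. For p from 10% to 40%, that is 90% to 60%.

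**3. Size under assumed rates**

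Both rates are assumptions; neither is in the documents.
- p = chance of a DLT in a patient without the last-row reaction: 10%, 20%, 30%.
- q = chance of the last-row reaction: 1%, 5%, 10%.

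With replacement, each evaluable patient has DLT probability p, so the result does not depend on q. If the reaction is counted, the probability is q + (1 − q)p. In both cases the quantity is the binomial P(X ≥ 3) with n = 6. For example, p = 20% and q = 5% give 0.05 + 0.95 × 0.20 = 0.24.

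| p | Replaced | Counted, q = 1% | Counted, q = 5% | Counted, q = 10% |
|---|---|---|---|---|
| 10% | 1.6% | 2.0% | 4.3% | 8.7% |
| 20% | 9.9% | 10.9% | 15.4% | 22.0% |
| 30% | 25.6% | 26.9% | 32.3% | 39.4% |

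The gap runs from 0.4 points (p = 10%, q = 1%) to 13.8 points (p = 30%, q = 10%). At q = 1% it is between 0.4 and 1.3 points. The chance that at least one of six patients has the reaction is 1 − (1 − q)^6, which is 6%, 26% and 47% for the three values of q.

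**Side check: the effect of 5.9 alone.** Suppose the DLT list stays as it is and the patient is kept as a non-DLT. The DLT probability is then (1 − q)p. At p = 30% and q = 5% this is 0.285, and P(X ≥ 3) is 22.8%, against 25.6% with replacement and 32.3% with counting. Replacement therefore makes the fallback more likely than keeping the patient as a non-DLT would.

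**The case against.** **Criterion 5 may already cover the case.** A patient barred from cycle 2 by a related reaction has not started it two weeks after it was due. Counting that patient is a fair reading. It does not help to reply that DLTs are judged at the end of cycle 1, since a delay of more than two weeks can never be known by then for anyone. This objection stands as far as it goes: the text is ambiguous. But the criterion speaks only of a delay, and 5.9 uses a discontinued infusion as its example of a patient without a DLT. Two assessors could classify the same patient differently.

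**The case is narrow.** A reader might infer that any grade 3 infusion reaction escapes the run-in count. The documents do not support that. The statement on 24-hour resolution covers reactions of all grades, while Table 5's grade 3 row includes prolonged reactions and hospitalization for sequelae, some of which will last beyond 3 days and count. Reactions that begin after 90% has been infused do not lead to replacement.

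**The event is not lost to safety reporting.** A reader might also infer that the toxicity disappears from the trial. It does not: Sections 8.1 and 8.2 analyse all enrolled patients for toxicity, and adverse events of grade 3 or higher are recorded.

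**Section 5.9 does not by itself bias towards the starting regimen.** It would be tempting to say that replacement can only lower the counted toxicity. The side check shows that this is wrong when the alternative is keeping the patient as a non-DLT. The loss exists only relative to counting the reaction, so it arises from 2.1.1.1 and 5.9 jointly.

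**Whether it should count is a design judgement.** No section says that treatment-ending toxicity must be a DLT. The replacement rule is explicit and may be deliberate, and the fallback leaves the amount of each MK-3475 infusion unchanged. That is fair. Still, the DLT list is not restricted to toxicities that the fallback would reduce, and the plan gives no reason for treating a delayed cycle 2 and an impossible one differently.

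**Conclusion.** The concern holds in a limited form. It needs a related grade 3 infusion reaction that stops the infusion before 90% and resolves within 3 days, and a reading of criterion 5 that excludes a cycle 2 never started. Under those conditions the six-patient gate omits a toxicity that the protocol itself treats as ending treatment, and one such event can decide between the two regimens.

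The likely size cannot be settled from the documents. Over the assumed ranges it is about 0.4 to 14 percentage points in the chance of more than 2 DLTs in 6, and about 1 point or less if the reaction rate is 1%. The ambiguity is worth removing because it affects the run-in's only formal decision and costs little to correct.

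**What to change.** Before the run-in evaluation, reconcile Section 2.1.1.1 (criteria 2 and 5), Table 5 and Section 5.9:
- State whether criterion 5 includes a cycle 2 that is never started because of a related toxicity, so that a related Cycle 1 toxicity that permanently ends trial treatment is handled consistently with it in the run-in decision.
- Qualify the infusion-reaction example in 5.9 accordingly, so that such a patient is not dropped by default. Replacement for under-exposure unrelated to toxicity can stay.
- Report the number of replaced patients, with reasons, beside the run-in DLT rate.

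Which toxicities count is for the investigators and the sponsor to decide; the need is for one consistent rule fixed in advance. Table 5 is unchanged.

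The cost is a short text change in two sections and one reporting line. If such events are counted, the fallback branch becomes somewhat more likely, by the amounts in the table above.

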5.10 Clinical Criteria for Early Trial Termination

Early trial termination will be the result of the criteria specified below:

- 1. Quality or quantity of data recording is inaccurate or incomplete
- 2. Poor adherence to protocol and regulatory requirements
- 3. Incidence or severity of adverse drug reaction in this or other studies indicates a potential health hazard to subjects
- 4. Plans to modify or discontinue the development of the study drug

In the event of Merck decision to no longer supply study drug, ample notification will be provided so that appropriate adjustments to subject treatment can be made.

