2.2 Trial Diagram

3.0 OBJECTIVE(S) & HYPOTHESIS(ES)

3.1 Primary Objective(s) & Hypothesis(es)

Objective: Determine the safety and tolerability of MK-3475 in combination with vorinostat patients with RMHNSCC and RMSGC

Hypothesis: The combination of MK-3475 and vorinostat is safe and well tolerated in patients with RMHNSCC and RMSGC

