4.2.3 Rationale for Endpoints

Both vorinostat and MK-3475 appear to be well tolerated as a single agents and have FDA approved doses and indications. These two drugs have non-overlapping mechanisms of action. There has been no reported clinical experience with the combination of vorinostat and MK-3475. Therefore a phase I/II design, wherein a limited phase I run in cohort is initially enrolled, was felt to be most appropriate to study this combination, with safety and tolerability as the primary endpoint of interest.

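### Safety is the primary endpoint, yet after the six-patient run-in the protocol states no numeric trial-level safety boundary for the remaining 64 patients

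*Combined protocol and SAP*

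**What the plan says.** Section 3.1 sets the primary objective ("Determine the safety and tolerability of MK-3475 in combination with vorinostat patients with RMHNSCC and RMSGC") and the hypothesis: "The combination of MK-3475 and vorinostat is safe and well tolerated in patients with RMHNSCC and RMSGC". Section 4.2.3 explains the choice: "There has been no reported clinical experience with the combination of vorinostat and MK-3475", hence a run-in design "with safety and tolerability as the primary endpoint of interest".

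Section 2.1.1 describes the run-in. "These initial 6 patients may come from either cohort", and they are assessed on cycle 1. The pass rule is: "If ≤ 2 of these six patients experience DLTs after completion of cycle #1, then the study will proceed to the phase II portion" on the starting regimen. With 3 or more DLTs, phase II opens on a lower vorinostat dose and a longer cycle. No DLT evaluation is described for that schedule.

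Section 2.1.2 takes enrolment to 35 per cohort, run-in patients included. From then on:

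- Section 5.10, item 3, is the trial-level safety criterion: "Incidence or severity of adverse drug reaction in this or other studies indicates a potential health hazard to subjects". It has no rate, denominator or review schedule.
- Section 8.2 tabulates toxicities as numbers and percentages. The only test in section 8.1 is on response, a secondary objective.
- Section 2.1.2.1 provides IRB and DSMC oversight, toxicity assessment every cycle and removal of individual patients. Section 7.2.3 requires SAEs and events of clinical interest to reach the sponsor within 24 hours. Section 10.5 places monitoring with the DSMC under an external plan, and section 10.6 adds weekly team review of adverse events.

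**The concern.** Six patients say little about a toxicity rate, and neither result of the run-in ends the trial. After it, the people who review safety data have no count or rate in this protocol that obliges them to act. The secondary endpoint has a cut-off (11 of 35 responses), whereas the primary hypothesis has no figure against which it could be judged.

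At stake is how many patients are treated before a high event rate leads to a formal decision. The gap is widest on the fallback schedule, which would be given to up to 64 patients without any DLT assessment of that schedule.

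**Working it through.** **Inputs.** Run-in n = 6, pass if 2 or fewer DLTs (2.1.1). Total 35 + 35 = 70, so 70 − 6 = 64 patients follow (2.1.2). The documents give no unacceptable DLT rate. True rates of 20% to 50% are therefore assumptions, constant over patients and cohorts.

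**The plan's own figures.** Section 8.1 gives operating characteristics for response only, and they reproduce: P(X ≥ 11 | 35, 0.20) = 0.075 (stated 0.07), P(X ≥ 11 | 35, 0.40) = 0.888 (stated 89%), and 1.96·√(0.25/35) = 0.166 (stated 17%). Nothing comparable is given for toxicity.

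**Run-in.** P(pass) = Σ C(6,k) p^k (1−p)^(6−k) for k = 0, 1, 2. At p = 0.40: 0.0467 + 0.1866 + 0.3110 = 0.544. An observed 2/6 has an exact 95% interval of 4% to 78%.

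**Expected DLT-type events if all 70 are enrolled after a pass.** E = E[X | X ≤ 2] + 64p. At p = 0.40: (0.1866 + 2 × 0.3110)/0.5443 + 25.6 = 1.49 + 25.6 = 27.1. The simpler 70p = 28 ignores that the run-in was passed.

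| True rate | P(pass) | Expected events in 70, given a pass |
|---|---|---|
| 33% | 68% | 1.36 + 21.3 = 22.7 |
| 40% | 54% | 1.49 + 25.6 = 27.1 |
| 50% | 34% | 1.64 + 32.0 = 33.6 |

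**Illustrative boundary.** The tolerated rate is taken as 1/3, from the protocol's own 2/6. The prior is Beta(0.667, 1.333). With x events in n patients the posterior is Beta(0.667 + x, 1.333 + n − x), and accrual pauses if P(rate > 1/3) > 0.90. At n = 12, x = 6 gives 0.859 and x = 7 gives 0.949, so the bound is 7. Bounds every 6 patients: 7/12, 9/18, 12/24, 14/30, 16/36, 19/42, 21/48, 23/54, 25/60, 28/66. If the count starts afresh on the fallback schedule (64 patients, looks at 6 to 60), the first bound is 4/6 and the others are the same. The probabilities below are exact, by convolving binomial distributions between looks.

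| True rate | P(pause), given a passed run-in | Mean enrolled of 70 | P(pause), fresh count on fallback |
|---|---|---|---|
| 20% | 0.2% | 69.9 | 2.2% |
| 25% | 1.4% | 69.4 | 6.1% |
| 30% | 6.4% | 67.6 | 15.8% |
| 33% | 14.6% | 64.9 | 27.5% |
| 40% | 46.2% | 54.3 | 61.1% |
| 50% | 91.4% | 33.9 | 95.5% |

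**Sensitivity.** With looks at 20, 30, 40, 50 and 60, tolerated rates of 30% or 33%, cut-offs of 0.90 or 0.95 and a prior worth one patient, the pause probability after a passed run-in is 25% to 65% at a true rate of 40% and 77% to 97% at 50%.

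**The case against.** The strongest reply is that safety review here is continuous and does not wait for a rate. The team meets weekly, serious events are reported within 24 hours, the DSMC and IRB oversee the study, and dosing is held, reduced or ended patient by patient. Item 3 of section 5.10 allows the trial to be terminated. All this stands. A reader might infer that the DSMC has no boundary to act on, or that an over-toxic regimen would be given to all 70 patients. The documents do not support either. The DSMC's monitoring plan is not among them, and the second inference supposes that every overseer declines to act. What can be said is that this protocol states no trigger.

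Nor do the documents call any DLT rate toxic. The DLT definition includes grade 3 events lasting more than 3 days and a delay of more than 2 weeks in starting cycle 2, so a DLT is not always a health hazard. The 33% to 50% range is an assumption.

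The illustrated rule has limits too. Its prior, cut-off and looks are choices. At a true rate of 40% it misses more often than it pauses, and it pauses by patient 24 in only 15% of trials. At 33%, the rate taken as tolerated, it pauses in 15%.

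Section 2.1.2 also speaks of ORR and PFS as belonging to the primary endpoint, against sections 3.1 and 4.2.3. That needs reconciling, but it would not remove the need for a safety boundary.

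**Conclusion.** The point holds for what this protocol states: after six patients there is no numeric trial-level safety boundary, in either branch, for a trial whose primary endpoint is safety. Over assumed true DLT rates of 33% to 50% the run-in takes the starting regimen forward 68% to 34% of the time, and completed enrolment would then include about 23 to 34 patients with a DLT-type event. A boundary of the kind illustrated would cut mean enrolment to about 34 at 50% and about 54 at 40%. The run-in probabilities are exact; the boundary's performance rests on the assumed 33% tolerated rate, the 0.90 cut-off and a constant rate across cohorts. The change should be made, but the existing oversight means that the trial is not without safety monitoring.

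**What to change.** Add to sections 2.1.2.1 and 8.1 a pre-specified boundary on cycle-1 events that meet the existing DLT definition, pooled over both cohorts and checked every 6 patients. Crossing it pauses accrual for DSMC review; it does not by itself end the trial. The sponsor and DSMC set the tolerated rate, and the table of operating characteristics goes into section 8.1. That rate also gives the primary hypothesis a figure. If the monitoring plan already holds a boundary, quote it instead.

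Three further changes belong with it:

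- If the fallback schedule is used, start the count afresh with the first patients treated on it.
- Reconcile item 6 of the DLT definition (2.1.1.1), which cites a Section 5.1.2.4 that does not exist; the haematologic rules are in 5.2.1.4.
- A cycle-1 count misses late events, and section 5.6.1.1 says that immune-related events can appear months after the last dose. Show the DSMC cumulative later-cycle grade 3 or higher events at each look.

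The cost is about half a page of text; toxicity is already assessed each cycle and grade 3 or higher events are recorded. The downside is an unneeded pause. After a passed run-in its probability is 0.2% at a true rate of 20%, 1.4% at 25%, 6% at 30% and 15% at 33%. It is higher with a fresh count on the fallback schedule: about 2%, 6%, 16% and 28%.
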